Subjects for this study will be recruited from the patient population seen by the investigators during the normal course of business. There will be no outside recruitment of individuals or advertising as to the presence or use of the monitoring device to entice new patient referral. Prospective candidates will be asked by the lead investigator at the time they are designated surgical candidates. All documentation related to the study will be reviewed with the patient by the lead physician or his designee who is appropriately trained in discussing patient recruitment. Final decision and randomization to control or StepRite use will be done as part of the preoperative checkup just prior to surgery where both operative consent and study consent are discussed and signed.

Randomization:

Once a patient agrees to the study they would be sequentially randomized into whether or not they receive StepRite. The patients will be randomized to every other eligible patient gets the intervention. (ie: 1,3,5,7,9... will get StepRite ; 2,4,6,8 will not get StepRite) 15 Intervention subjects will be recruited and 15 control subjects will be recruited with an extra 5 patients to account for attrition and withdrawals.

Schedule of events

The intervention group will receive the StepRite device with standard conventional care and the control group will receive standard conventional care only. Both groups will receive outpatient, home health, and /or 24 hour physical therapy treatment plans per their surgeon's standard of care. The control group will undergo the conventional outpatient treatment program to 8 weeks as normally prescribed by the lead investigator. This consists of a twice weekly outpatient appointment with a physical therapist and prescribed home exercise program (see attached physical therapy protocol).

The patients randomly selected to wear the StepRite inserts will be fitted and instructed along with the patient's designated care giver in their use including initial pre-op measurements prior to their surgical date so that data collection can begin on the 1st day of rehab after surgery

Those patients not selected to wear step rite will receive instructions preoperatively of their expected therapy regimen and receive their baseline functional evaluation of the knee

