Both groups will be given log sheets to record their activity at home and when seen by the physical therapist. These will be returned and collected by the therapist weekly and scanned into/ kept in the patient's medical record file. A paper copy will be kept in the coordinator's office, 4A144B with the consent forms and any other study documents.

Both groups will also have routine self-assessment questionnaires (appendices 3, 4 KOOS and KSS) and functional testing performed by the PI and PT during the patient's regular clinic visit as standard of care.

Outcome measurements performed just after surgery and at time of discharge from hospital and standard of care post-surgical clinic visits to 8 weeks will indicate if any patients are experiencing unexpected delays in progress. Subjects will be visited at home by the Home Health therapists, and will visit and receive telephone consultations with the outpatient therapists, who will be able to monitor the patients' conditions and intervene if there are any problems related to the use of the device. The StepRite device will provide the therapist with more information about the patients' activity levels and progress than would usually be available to them and so is not expected to have any safety implications. The device and App. will prompt the patient with voice and text to complete their exercises as they are needed, while collecting data.

Device Flow Chart: standard of care post-op

The research coordinator will consent the patient prior to the surgery

The research coordinator will document the following information for the device on the device data collection form. (See attached)

- a. Name of patient
- b. Email of patient
- c. Phone number of patient
- d. Surgery date
- e. Expected date of discharge

The patient's information will then be entered into the steprite™ system and a patient account will be created by the Research Coordinator

Physical therapy will schedule the study protocol via the steprite™ system and enter the physical therapy start date as day after discharge.

MedHab™ sponsor ([name]) will contact the patient for the patient account set up and to obtain the following signatures required by MedHab (see attached)

- a. HIPAA
- b. Assignment of Benefits

MedHab™ will help the patient load the app, provide an overview of the app, and forward a tutorial video
MedHab™ will send the steprite™ device to the study Research Coordinator at TTUHSC

TTUHSC Orthopaedic Surgery

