Clinical Trials Coordinator, [name]

[name]

(t)[contact] (f)[contact]

The Research coordinator will fit the patient with the device, pair, and connect the device at time of discharge.

Patient will leave the hospital with the steprite™ device and instructions to charge device overnight for use the next day.

Patient will begin exercise regimen prompted by the StepRite App on the cell phone.

Physical therapy will communicate with the patient per the therapy protocol

Physical therapy is to work with patient per standard of care protocol with the addition of 3 patient outcome surveys, (KOOS, KSS, and the Lower Extremity functional scale) (see attached) at 4, 6, and 8 weeks post op, and the PI will see the patient as standard of care at visits 2, 6, and 12 weeks post-op. The 2 week patient outcome surveys will be completed at the 2 week standard clinic visit with the assistance of the study coordinator. All documents and data collection forms from physical therapy and clinic will be

scanned into the patients chart for review and kept in a locked file cabinet in the research coordinators office 4A144B.

Physical therapy advises the PI and MedHab two weeks prior to close of therapy on close out or extension procedure if needed.

The PI and MedHab extends the therapy or communicates the close out procedure with the patient.

Control Subject flow

The control group will have all Post-op standard of care as the device group without the use of the device.

Device Information

The device to be used in the study is the StepRite, manufactured and supplied by Medhab LLC. The device is considered exempt from IDE regulations, as it is a diagnostic device. It has been approved as a Class I medical device by the FDA.

The StepRite device consists of a thin insole which is placed inside the shoe.

The insole contains pressure sensors which record pressure data when exercises are performed, and contains an accelerometer, which records acceleration of the foot and is used to calculate velocity and activity levels.

A wireless connection between the insole and a cell phone application allows transfer of data.

The cell phone application will be supplied.

The cell phone application displays real-time feedback of pressure distributions to the user, and connects wirelessly to the Medhab servers to upload data onto the secure web interface, for access by the physical therapist or physician.

The device does not impart energy to the user.

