The patient or designated care giver will be responsible for placing the insoles on their charging platform nightly.

Indicate the number of patients/charts/surveys/specimens needed.

The total number of patients needed in this study is 30, we will request a total of 35 to account for possible Attrition or withdrawals. 15 will be fitted with the StepRite device and 15 will follow the normal postoperative protocol without the device and be considered control subjects.

Inclusion criteria

Unilateral Partial or Total knee arthroplasty.

Age 45-75 yr. old

BMI <35

Access to Wi-Fi

Have appropriate smart phone and knowledge of use

Be willing to place StepRite app on their personal phone

Exclusion criteria

History of neuromuscular disorder (e.g. Parkinson's, Polio, or stroke).

Pregnancy

History of cognitive disease that would preclude ability to navigate smart phone

Method of identifying and recruiting subjects.

Recruitment will come from the investigators normal patient population who are scheduled for a partial or total knee replacement. The Investigators will identify and consult the research coordinator to assess eligibility.

Compensation given to subjects.

There will be no compensation given to subjects. They will be allowed to keep the insoles and access the app for at home therapy at no cost to them for as long as the device works.

Describe the site(s) where study will be done.

The main clinical/surgical portion of the study will take place at Texas Tech University Health Sciences Center department of Orthopaedic Surgery and University Medical Center Lubbock. The physical therapy departments used for this study will be the investigators preferences and standard of care, therefore they would be used if not on the study and are not study specific.

MedHab LLC (StepRite) will be collecting data from several sites to compare outcomes and cost. The secondary sites utilizing this device and doing similar studies are Covenant with [name] as the lead investigator, the Lubbock Heart Hospital with [name] as the lead investigator, and Texas Health Resources with [name] as lead investigator. All the secondary sites will use their standard of care preferences for clinical/surgical and physical therapy. TTUHSC will not be collecting data nor in any way be affiliated with the secondary study sites. They will acquire their local IRB approval for each site separately using similar device protocols.

Risks

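### App loading, pairing and the manufacturer's signatures come after allocation and only in the StepRite arm, and no rule keeps a patient who fails them in the comparison

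*Combined protocol and SAP*

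**What the plan says.** Everything here is in the combined protocol and SAP.

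- **Inclusion criteria (all patients).** "Access to Wi-Fi"; "Have appropriate smart phone and knowledge of use"; "Be willing to place StepRite app on their personal phone". The exclusion criteria add cognitive disease that would prevent use of a smart phone. Under the recruiting section, "The Investigators will identify and consult the research coordinator to assess eligibility", with no distinction by arm.
- **Allocation.** The Randomization section alternates among patients already judged eligible: "The patients will be randomized to every other eligible patient gets the intervention". On timing, the recruitment text says: "Final decision and randomization to control or StepRite use will be done as part of the preoperative checkup just prior to surgery". Study consent is signed at the same visit.
- **Device flow chart (StepRite arm only).** After consent and account creation, the manufacturer "will contact the patient for the patient account set up and to obtain the following signatures required by MedHab". The two forms are HIPAA and Assignment of Benefits. The manufacturer then helps the patient load the app. Later, "The Research coordinator will fit the patient with the device, pair, and connect the device at time of discharge".
- **Control Subject flow.** The same postoperative standard of care without the device. No account, app, signature or pairing step is listed.
- **Number of patients.** 30 are needed and 35 requested to allow for attrition or withdrawal. The StepRite target of 15 is described by fitting of the device.
- **Risks.** Subjects may withdraw from the study at any time and return to conventional rehabilitation. The two are named together.
- **Analysis.** A two-group t-test. No analysis population is stated, and there is no rule for a patient whose device set-up fails.

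**The concern.** An allocated comparison is protected only if the same kinds of patient remain in both arms. Here a StepRite patient faces hurdles after allocation that a control never meets: two manufacturer forms, an app that has to load on that patient's phone, and an insole that has to pair with it. If a patient who stops at one of these steps leaves the study or goes unanalysed, the StepRite arm loses that type of patient while the control arm keeps its equivalents.

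Patients who manage the technology and paperwork may also be the ones who keep up their exercises. If so, the loss would favour StepRite without any device effect. That direction is plausible, but the documents contain no evidence on it.

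**Working it through.** **1. The plan's own figures.** 15 + 15 + 5 = 35, which agrees with the 35 requested. The implied attrition is 5/35 = 14.3%. The 30 itself cannot be re-derived, because no effect size or SD is given.

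**2. Order of events.**

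| Step | StepRite | Control | Relative to allocation |
|---|---|---|---|
| Phone, knowledge of use, Wi-Fi, willingness to install | yes | yes | before |
| HIPAA and Assignment of Benefits signatures | yes | no | after |
| App actually loaded | yes | no | after |
| Insole fitted and paired | yes | no | after |

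The three *after* entries follow from the text: allocation happens at the consent visit, the chart lists these steps after consent, and only StepRite patients follow the chart. The timing of fitting is inconsistent. Schedule of events puts fitting and pre-operative measurements before the surgical date, whereas the flow chart puts fitting and pairing at discharge. Both come after allocation.

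**3. What happens to a patient who fails a step.** Nothing says the patient is removed, replaced or declared ineligible, and nothing says the patient is kept. Two passages lean towards loss. A target counted by fitting does not count a patient who is never fitted. The Risks text couples return to conventional care with leaving the study.

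**4. Size of the bias if such patients are lost.** Let a fraction f of each arm be of this type, with a mean δ SD below the rest, whose mean is m.

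- Control keeps them: mean = (1 − f)m + f(m − δ) = m − fδ.
- StepRite loses them: mean = m.
- Difference with no device effect: f × δ.

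Both inputs are assumptions; the documents give neither.

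| f | δ = 0.5 SD | δ = 1 SD |
|---|---|---|
| 10% | 0.05 SD | 0.10 SD |
| 20% | 0.10 SD | 0.20 SD |

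**5. Effect on the test.** At 15 per arm the standard error is √(2/15) = 0.365 SD. For a two-sided 5% test (sidedness is not stated in the plan; normal approximation, SD taken as unchanged by the loss), the false-positive rate under a bias b is Φ(b/0.365 − 1.96) + Φ(−b/0.365 − 1.96).

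- b = 0.05: 0.052.
- b = 0.20: 0.085.

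For scale, the difference detectable with 80% power at 15 per arm is (1.96 + 0.84) × 0.365 ≈ 1.02 SD, or about 1.06 SD by the t distribution.

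**6. Precision.** Alternating 35 patients with StepRite first gives 18 v 17. An f of 10–20% of 18 is 1.8 to 3.6, so about 2 to 4 patients.

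- Lose 3: 15 v 17, SE = √(1/15 + 1/17) = 0.354 SD.
- Lose 4: 14 v 17, SE = √(1/14 + 1/17) = 0.361 SD.

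Both are below the planned 0.365, so the extra patients absorb the loss. They do not remove the bias.

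**7. If set-up failures are followed up and analysed as allocated**, both arms have mean m − fδ and this bias is zero.

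**The case against.** The strongest case against is that technology ability is already screened in everyone. The phone, knowledge, Wi-Fi and willingness criteria, and the cognitive exclusion, apply to both arms before allocation. The manufacturer helps load the app and the coordinator does the pairing, so failures may be few. The recruitment text says all study documentation is reviewed with the patient, and the manufacturer's forms are attachments to the protocol, so a reluctant patient may see them and decline before allocation. The flow chart describes delivery of the device, not eligibility. Finally, one sentence requiring analysis as allocated would remove the bias, so a check in every control could be called optional.

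Much of this stands. A reader might infer that phone compatibility is examined only in the StepRite arm, that controls are unselected, or that a different eligibility screen is applied to each arm. The documents do not support any of these: the criteria are common to both arms, and no passage makes a set-up failure ineligible. Nor do they support a loss of precision.

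What remains is narrower. An appropriate phone is not defined, and nothing before allocation shows that the app installs or the insole pairs. Willingness to sign the Assignment of Benefits form is not a criterion, and the text on document review does not name the manufacturer's forms. The handling of failures is unstated. Analysis as allocated does cure the bias, but it leaves untreated patients in the StepRite arm and dilutes any effect. An earlier check reduces that dilution.

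**Conclusion.** The point holds as a risk, not as a demonstrated defect. The device-only steps follow allocation, and no rule keeps a patient who fails or declines them in the comparison, so one-sided loss is possible.

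Its size cannot be known from the documents. The range of 0.05 to 0.20 SD rests on an assumed 10–20% failure rate, an assumed deficit of 0.5–1 SD, and the assumption that failures are dropped. The low end is negligible. The high end is about a fifth of the difference this trial could detect (0.20/1.02). The bias would favour StepRite only if those lost would indeed have done worse. It is a modest, conditional problem, worth fixing because prevention is cheap.

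**What to change.** 1. Before the arm is revealed, have every patient review the manufacturer's HIPAA and Assignment of Benefits forms and confirm willingness to sign if allocated StepRite.
2. At the same visit, confirm on the patient's own phone that the app installs, and that it pairs if a demonstration insole is available.
3. Add both to the inclusion criteria and record the result before the patient takes a place in the allocation sequence. Alternation makes the next arm predictable, so this limits selective judgement but does not give concealment; that needs a separate change.
4. State that every allocated patient is followed up and analysed in the allocated arm, including one who later declines to sign or whose set-up fails.
5. Count the 15 per arm by allocation, not by fitting, and separate stopping the device from withdrawing from the study.
6. Reconcile Schedule of events with the device flow chart on when fitting and pairing take place.

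The cost is likely to be a few minutes of coordinator time per patient at an existing visit, and a few patients screened out before allocation. The manufacturer would need to supply its forms, and app access for the check, earlier than the flow chart now has it. Items 4 and 5 need only wording and continued follow-up.

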The StepRite system developed by MedHab (<http://www.medhab.com/>) allows the physical therapist to monitor physical activity and exercise remotely, thereby reducing the need for frequent out-patient visits. A thin insole placed inside the shoe measures foot contact pressure and acceleration. This information is translated into quantitative feedback about exercise compliance and performance measures comparing the surgical side with the non-surgical side. Real time feedback during exercise and weight-bearing activities is

provided to the patient, and a HIPAA secured user interface website also displays this information in an online dashboard for both physical therapists and the physician.

With the advent of federally mandated bundled payments for total joint replacement, active management of the rehabilitative process postoperatively with quantifiable data will be necessary to ensure financial stability.

Given the potential for improving patient engagement with rehabilitation, this study proposes a treatment model which includes monitoring activity outside of the clinic using the StepRite device and using a combination of outpatient appointments and remote consultations with therapists.

Significance of this study

The significance of the proposed study includes the projected benefit to the patients in terms of attaining clinical outcomes quicker and to the medical system in terms of managing cost for the provision of services. Subjects are expected to demonstrate improved compliance to patient tailored rehabilitation protocols which will lead to more rapid attainment of clinical outcomes versus present traditional rehabilitation methodologies. The expected level of, and rate of, attainment of clinical outcomes will translate to an overall reduction of cost to the medical system by reducing the need to engage in additional processes or the need to protract the time required to attain clinical outcomes, where either or both in combination can increase rehabilitation expenditures.

Objectives

To compare the efficacy of StepRite in a prescribed physical therapy program verses traditional in-facility physical therapy program after partial or primary total knee replacement using validated survey tools to evaluate patient progress, including patient self-reporting of progress and surgeon appraisal of patient performance post-operatively.

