There is a risk of loss of confidentiality, we will have measures in place to help prevent any loss of personal information. During the course of this study there are no new or additional steps required of the subjects from what is considered the standard protocol for the lead investigator. The only alteration may be reduced travel and outpatient visit by the patient if compliance and functional improvement noted by the therapist. StepRite imparts no energy to the patient and poses no hazard to patient well being. Subjects will be free to withdraw from the study at any time and revert to conventional rehabilitation treatment.

Possible benefits to subjects

There is a possibility the device group patient could benefit from the device prompting them to do their own exercises regularly, which could lead to a faster recovery and better physical therapy outcomes. We are hoping the participation in this study may help us learn how we can design rehabilitation programs to be more effective in the future.

Confidentiality measures

StepRite / MedHab will have access to non-PHI patient data collected by the device stored on their HIPPA compliant server and be available only to the lead investigator. All PHI will be kept separate from the study data in a locked filing cabinet or on a password protected computer in the research coordinators office in 4A144B.

Data Collection and Monitoring

Data recorded by the StepRite device will be transmitted wirelessly to the HIPAA secured web interface managed by Medhab. Clinicians will be able to log into the website with a password to review the progress of each patient.

Data recorded by the PI and physical therapist on the functional motion of the knee will be recorded in paper form and kept with the completed KOOS questionnaire and Knee Society Score (KSS) and scanned into the patients HIPPA protected chart.

Upon completion of patient's part in the study MedHab will contact UMC and the Therapy departments to acquire actual costs of these services. This will be done to compare the overall cost of management of the post-operative rehabilitation of a patient in traditional rehabilitative regimen vs. use of StepRite,

Actual Cost information for the patient's full rehabilitation will be requested and collected by the Hospital and released to MedHab at the end of the study and supplied to the lead investigator for analysis.

References

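### Survey collection at weeks 4 and 8, and LEFS after week 2, rests on therapy attendance, which may fall with good progress mainly in the StepRite arm

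*Combined protocol and SAP*

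**What the plan says.** All references are to the combined protocol and SAP.

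- **Who collects the surveys.** Under Device Flow Chart: standard of care post-op, the text reads "Physical therapy is to work with patient per standard of care protocol with the addition of 3 patient outcome surveys" (KOOS, KSS and LEFS), due "at 4, 6, and 8 weeks post op". Week 2 is handled differently: "The 2 week patient outcome surveys will be completed at the 2 week standard clinic visit with the assistance of the study coordinator".
- **Surgeon visits.** In the same section, "the PI will see the patient as standard of care at visits 2, 6, and 12 weeks post-op".
- **Device-arm attendance.** The Background presents remote monitoring as "thereby reducing the need for frequent out-patient visits" and describes a model "using a combination of outpatient appointments and remote consultations with therapists". The Risks section adds: "The only alteration may be reduced travel and outpatient visit by the patient if compliance and functional improvement noted by the therapist".
- **Control-arm attendance.** Schedule of events gives controls a conventional outpatient programme to 8 weeks: "This consists of a twice weekly outpatient appointment with a physical therapist and prescribed home exercise program". It also allows home health and other therapy settings in both groups.
- **Same regimen.** Study Design and Methods says the device arm follows the control regimen with StepRite added, and that postoperative care is otherwise unchanged apart from monitoring and enforcing the home programme.
- **Other contacts.** Schedule of events has KOOS and KSS done at regular clinic visits in both groups, without naming LEFS. It also mentions weekly log returns, home visits and telephone consultations, but assigns no survey to them.
- **Analysis.** Study Design and Methods names a two-group t-test. No rule for missing surveys is given.

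**The concern.** Three of the four dated survey rounds are attached to therapy contact. The intervention is expected to reduce that contact, and the stated condition for reducing it is good compliance and functional improvement. If a reduced schedule leaves a device patient without a therapy visit around week 4 or week 8, the form most likely to be lost is that of a patient who is doing well. No comparable reduction is described for controls.

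Missingness of that kind depends on the outcome and differs by arm, and a complete-case t-test does not correct for it. It would also set the trial's two objectives against each other: the more StepRite cuts visits, the less securely function is measured. Fewer visits with no apparent functional gain could then not be told apart from a true lack of effect.

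**Working it through.** **1. Which survey points are exposed**

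| Week | Route in the flow chart | Surgeon visit that week? | Exposed to therapy attendance |
|---|---|---|---|
| 2 | Clinic visit with coordinator | Yes | No |
| 4 | Physical therapy | No | KOOS, KSS, LEFS |
| 6 | Physical therapy | Yes | LEFS (KOOS and KSS can be taken at the clinic visit) |
| 8 | Physical therapy | No | KOOS, KSS, LEFS |

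Week 8 is the last survey with a stated date.

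**2. The plan's own figures**

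The plan gives no figure for this risk. Its sample size of 15 per arm is offered as a starting point, with no effect size or SD, so it cannot be reproduced. Solving backwards with a two-sided t-test (sidedness is not stated), alpha 0.05 and 80% power, 15 per arm detects a difference of 1.06 SD. The request for 35 patients agrees with 30 / (1 - 5/35) = 35. Extra patients would restore numbers, but they would not remove a bias that comes from which patients are missing.

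**3. Size under stated assumptions**

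Take normal scores with SD 1. Let f be the best-scoring fraction of device patients and m the share of them who miss the survey, with no loss in controls. Both f and m are assumptions. The device mean among those observed shifts by

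shift = -m × φ(z) / (1 - m × f), where z is the (1 - f) quantile of the standard normal.

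- f = 0.20: z = 0.842, φ(z) = 0.280. With m = 0.25, the shift is -0.25 × 0.280 / 0.95 = -0.07 SD. With m = 1, it is -0.280 / 0.80 = -0.35 SD.
- f = 0.33: z = 0.440, φ(z) = 0.362. With m = 1, it is -0.362 / 0.67 = -0.54 SD.

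Power comes from 40,000 simulated trials of 15 against 15, analysed by complete-case t-test, with a true difference of 1.06 SD. Expected forms lost is 15 × f × m.

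| f | m | Forms lost of 15 | Shift (SD) | Power |
|---|---|---|---|---|
| none | 0 | 0 | 0 | 80% |
| 20% | 25% | 0.75 | -0.07 | 75% |
| 20% | 50% | 1.5 | -0.16 | 68% |
| 20% | 100% | 3 | -0.35 | 50% |
| 33% | 25% | 1.2 | -0.10 | 71% |
| 33% | 50% | 2.5 | -0.22 | 59% |
| 33% | 100% | 5 | -0.54 | 27% |

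These shifts assume that the patients who miss are ranked exactly by the survey score. If the progress noted by the therapist correlates only 0.5 with the score, each shift halves, and the range becomes -0.04 to -0.27 SD.

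**The case against.** A reader might infer that outcomes will go missing in the patients StepRite helps most. The documents do not support that.

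- The Risks section says only that visits may be reduced, and fewer visits is not none: half of a twice-weekly schedule is still weekly. The survey dates are set by calendar, and nothing waives them.
- Study Design and Methods and Schedule of events promise device patients the standard regimen, and the sentence that assigns the surveys says the same. At most the passages conflict on whether attendance differs.
- It is tempting to add that good responders close out of therapy early. The flow chart covers close-out or extension, with no timing and no link to response.
- It is equally tempting to say that controls always have a visit at the survey weeks. Both groups may have home health, so controls can lack an outpatient visit too. The dated surveys also sit in the device flow chart, while Control Subject flow refers only to standard care, so control completion is not assured either.
- KOOS and LEFS are self-reported, weekly log returns and telephone contact are planned, and the hypothesis lists the instruments as alternatives or in combination.
- No week-8 analysis is specified, and the hypothesis refers to 3 months. The therapy protocol is an attachment that was not available here and may contain a collection instruction.

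These points remove any claim of certainty and make the direction of bias conditional. They do not close the gap. Available contacts are not an assigned collection route, the surgeon visits miss weeks 4 and 8, and the text makes reduced visits conditional on doing well and describes this only in connection with device use.

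**Conclusion.** The concern holds as a risk. Collection of all three instruments at weeks 4 and 8, and of LEFS at every time after week 2, depends on attendance that may fall with good outcome mainly in the device arm, and the available text states no alternative route. KOOS and KSS at week 6 can be covered by the surgeon visit.

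The documents give no rate of visit reduction or survey loss, so the size cannot be derived from them. Under the assumed range (25% to 100% of the best 20% to 33% of device patients missing, no control loss, ranking by the score itself), the bias is about -0.07 to -0.54 SD, against the device. Power for a true difference of 1.06 SD falls from 80% to between 75% and 27%. The lower end is modest, and the upper end requires every one of the best third to be lost. Neither end is a forecast. The change is still worth making before data collection, because it is cheap and a form missed at its due date cannot be recovered later.

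**What to change.** 1. State that KOOS, LEFS and the patient-completed part of KSS are due in every patient, in both arms, at weeks 2, 4, 6 and 8 within a stated window, whatever the therapy status. Put this where it plainly applies to controls as well as device patients.
2. Where no visit falls in the window, have the research coordinator obtain the form by phone, e-mail or post and record the mode of completion.
3. Take the surgeon-rated part of KSS at the surgeon visits at weeks 2, 6 and 12.
4. Record contact details for controls too. The flow chart provides for e-mail and phone only on the device data collection form.
5. Reconcile the passages that foresee fewer outpatient visits (Background, Risks) with those that promise the same regimen (Study Design and Methods, Schedule of events), so that expected attendance in each arm is clear.

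The cost is protocol wording and a few coordinator contacts. The downside is that some forms will be completed remotely, so completion mode is mixed and may differ by arm; recording it lets this be examined. The change does not settle whether a survey is needed at the 3-month point named in the hypothesis, which is a separate matter.
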